## **6.0 MEASUREMENT OF EFFECT**

The main effect we will measure to achieve our primary objective is the treatment effect (proportion of dead tissue - benign and cancerous) inside the TMA-treated zone on the prostatectomy specimen. The excised prostate will be sliced at 4 mm intervals. Each slice will be embedded, and a pathologist will examine slides corresponding to each slice. The pathologist will be blinded to MR and TRUS imaging results. TTC and/or H&E staining are performed to determine thermal ablation zone size/location/relationship to urethra seminal vesicles capsule and other structures.

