## **2.1 Primary Objectives**

To determine the feasibility of transperineal targeted microwave ablation of an MRI-identified index prostate cancer in patients undergoing radical prostatectomy.

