## **2.4 Primary Endpoints**

The ablated area on the radical prostatectomy specimen assessed by viability tissue staining (TTC).

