## **2.5 Secondary Endpoints**

- The intra/post-operative safety of the targeted microwave ablation (number and severity of device- and procedure-related adverse events,
- TMA procedure duration: probe-in / probe-out time, ablation time
- Comparison between the ablation location in the prostate as seen in the KOELIS 3D map and the ablation location observed histologically on the prostatectomy specimen
- The change in urinary functions between baseline and each follow-up visit, using IPSS score and uroflowmetry
- The change in erectile functions between baseline and each follow-up visit, using IIEF-5 score
- The change in quality of life between baseline and each follow-up visit, using EPIC-26 score
- The correlation between the treatment effect dimensions measured histologically on the prostatectomy specimen resected after TMA, compared to the predictive ablation charts provided by the manufacturer
- The correlation between the treatment effect dimensions measured histologically on the prostatectomy specimen resected one month after TMA, compared to post TMA dimensions measured on the pre-RP mpMRI.
- Evaluation of the optimal treatment parameters to maximize the cell destruction without causing collateral damage.

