##### **4.4.2 Duration of Therapy**

One session (one entire TMA procedure consisting of one to two ablations in accordance with TMA delivery protocol) only.

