#### **10.3 Primary Objective Statistical Considerations**

To determine the feasibility of transperineal targeted microwave ablation of an MRI-identified index prostate tumor in patients undergoing radical prostatectomy, we will evaluate the viable tissue remaining after TMA using histologic examination of excised prostate specimen.

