#### **10.4 Secondary Objective Statistical Considerations**

The intra-operative safety of the targeted microwave ablation, the number of microwave ablations needed to ablate one mpMRI-visible lesion, the ease of use of the operative procedure and the feasibility of the immediate or 1 mo delayed radical prostatectomy after the targeted microwave ablation will also be evaluated.

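### Ablating the index tumour is the primary objective, but no listed endpoint measures how much of that tumour was ablated

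*Combined protocol and SAP*

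**What the plan says.** The primary objective in Section 2.1 is "To determine the feasibility of transperineal targeted microwave ablation of an MRI-identified index prostate cancer in patients undergoing radical prostatectomy". The measures meant to serve it are these:

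- **Primary endpoint (2.4):** the ablated area on the specimen, read by TTC.
- **Main effect (6.0):** "the treatment effect (proportion of dead tissue - benign and cancerous) inside the TMA-treated zone on the prostatectomy specimen". The same section adds: "TTC and/or H&E staining are performed to determine thermal ablation zone size/location/relationship to urethra seminal vesicles capsule and other structures". The tumour is not among the structures named.
- **Primary statistical consideration (10.3):** "we will evaluate the viable tissue remaining after TMA using histologic examination of excised prostate specimen". No region, tissue type or denominator is given.
- **Targeting endpoint (2.5):** "Comparison between the ablation location in the prostate as seen in the KOELIS 3D map and the ablation location observed histologically on the prostatectomy specimen". Section 10.7 says only that these locations will be recorded.
- **Chart and mpMRI endpoints (2.5, 10.7):** histologic ablation dimensions against predicted or imaged ablation dimensions.

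Section 10.4 also plans to evaluate "the number of microwave ablations needed to ablate one mpMRI-visible lesion", while Section 4.4.2 fixes treatment as "One session (one entire TMA procedure consisting of one to two ablations in accordance with TMA delivery protocol) only". Section 4.2 assigns five templates by order of enrolment. It allows physician modification to avoid collateral damage and for safety. Neither the Study Summary nor Sections 3.1 and 3.2 set a limit on lesion size.

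**The concern.** The objective is about a tumour; the measures are about an ablation zone. The two coincide only if the zone contains the tumour, and nothing listed checks that. The rationale in Section 1.3 itself names inaccurate targeting and inadequate ablation as the two ways in which current focal therapy leaves cancer behind. The listed measures address the second, and the first only in part.

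Section 10.1 says the study should show whether TMA is promising as a stand-alone local treatment. A report of nearly complete in-zone necrosis would be read as support for that, even if part or all of the index tumour lay outside the zone. Without a prespecified coverage measure, any later statement about the index tumour would be post hoc.

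**Working it through.** The plan gives no target, threshold or power for the ablation measure (Section 10.6 sets 15 men on practical grounds), so there is no figure of its own to reproduce. The check has three parts.

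**1. What each measure refers to.**

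| Measure | Quantity | Reference or denominator |
|---|---|---|
| 2.4 primary endpoint | ablated area | none stated |
| 6.0 main effect | dead tissue, benign and cancerous pooled | treated zone |
| 2.5 targeting | ablation location on histology | ablation location on 3D map |
| 2.5 charts | ablation dimensions on histology | chart dimensions |
| 2.5 mpMRI | ablation dimensions on histology | ablation dimensions on MRI |

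The index tumour is absent from the last column. The nearest item is the ablation count in 10.4. It is not a listed endpoint, and no section says when a lesion counts as ablated.

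**2. What the treated zone could mean.** Section 6.0 does not define it.

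- If it is the zone planned on the fused image, a needle that strays from plan lowers the score. A fusion error, or a lesion larger than the zone, does not.
- If it is the zone seen on histology, the measure is close to circular.

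On either reading a missed or under-covered tumour can coexist with the maximum value.

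**3. Size, for illustration.** Section 4.2 gives the chart zones (short x long axis): 1.5 x 2.5 cm at 3 min, 2.0 x 2.7 cm at 5 min and 2.5 x 3.0 cm for the long ablation (7.5 min in the templates). My assumptions are a spherical lesion, an ellipsoidal zone, any offset along the short axis, and all tissue in the zone dead, so that in-zone necrosis reads 100% throughout.

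Take a centred 2.0 cm lesion in the 3-min zone, with z the distance in cm from the centre along the antenna. The squared radius of the zone is 0.5625(1 − z²/1.5625) = 0.5625 − 0.36z²; that of the lesion is 1 − z². The zone is the narrower up to z = √(0.4375/0.64) = 0.827. Then

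overlap/π = 2[∫₀^0.827 (0.5625 − 0.36z²)dz + ∫_0.827^1 (1 − z²)dz] = 2(0.397 + 0.028) = 0.851,

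and the lesion volume/π is 4/3 = 1.333. Coverage is 0.851/1.333 = **64%**.

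Two simpler figures mislead. The ratio of volumes, (π/6 × 1.5² × 2.5)/(π/6 × 2.0³) = 2.95/4.19 = 70%, is only a loose upper bound, because the ends of the zone project beyond the lesion. The ratio (1.5/2.0)² = 56% holds only in the section perpendicular to the antenna; in a section along the antenna, coverage is 81%.

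Simulated coverage (400,000 points per lesion) for other assumed sizes and offsets:

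| Zone | Lesion | 0 mm | 5 mm | 10 mm | 15 mm |
|---|---|---|---|---|---|
| 3 min | 10 mm | 100% | 78% | 12% | 0% |
| 3 min | 15 mm | 100% | 60% | 18% | 0% |
| 3 min | 20 mm | 64% | 47% | 19% | 2% |
| 5 min | 15 mm | 100% | 87% | 39% | 5% |
| 7.5 min | 15 mm | 100% | 100% | 65% | 19% |

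Templates 1 and 2 place one ablation in each lobe. They are assigned to patients 1, 2 and 6 to 9, that is 6 of 15 men. Unless the lesion crosses the midline, one of the two ablations in each of these men lies away from it, yet it can add to the ablated area.

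**The case against.** The in-zone measure fits several stated aims. Hypothesis 1 speaks of killing cancer in the treated area, and question 1 in Section 1.6 of eradication within the ablated area. Section 7.1 says that treatment is not curative, is conservative and escalates in size, so partial coverage is to be expected, and the bilateral templates also serve to characterise tissue effect. Whole-mount H&E is planned for every man, with pre-prostatectomy MRI and biopsy in the delayed phase. All of this stands. It explains why partial coverage may be accepted; it does not explain leaving coverage unmeasured when the objective names the index cancer.

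The documents do not support four stronger readings:

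- **That a missed tumour would be declared a success.** There is no success threshold for ablation. The only numeric rule (7.7, 10.7) concerns severe adverse events. The measure can reach its maximum, and no more than that can be said.
- **That an antenna 1 cm off target would give perfect map-to-histology agreement.** The Study Schema compares histology with the predicted ablation on the 3D map. If that is the plan drawn on the fused lesion, a stray needle shows as a mismatch. If it is the actual antenna position, the two agree. The plan does not say which.
- **That energy failure would go undetected.** Viable tumour inside the zone lowers the Section 6.0 measure. Only the coverage half is missing.
- **That the count of ablations needed is beyond observation in any form.** Templates 3 to 5 contrast single with double ablations, and the Study Summary allows extension to further parameters. As planned, though, the count is set by template at one or two, and an ablated lesion is undefined, so the item cannot be evaluated.

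**Conclusion.** The point holds as a gap in endpoint definition: the primary measure can be maximal while the index tumour is missed through fusion error or under-covered by a preset template. The size depends on lesion diameters and offsets that the documents do not give. At 10 mm offset, over assumed lesions of 10 to 20 mm, coverage is 12–19% for the 3-min zone, 35–43% for the 5-min zone and 55–80% for the 7.5-min zone. Centred lesions of 10 or 15 mm are fully covered by all three, so under-coverage is possible, not inevitable. The overlapping double ablations of Templates 4 and 5 were not modelled. The specimens needed to close the gap already exist within the plan; what is missing is the endpoint and its definitions.

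**What to change.** In Sections 6.0, 10.3 and 2.5, add a descriptive endpoint for each fully evaluable man, reported separately by resection phase:

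- **(a)** The percentage of histologic index-tumour area, summed over the whole-mount slices, that is non-viable. In the immediate phase, overlay the H&E tumour outline on the TTC viability of the same slice, since TTC is read macroscopically. In the delayed phase use H&E, with a stated rule for slices where necrosis or fibrosis obscures the original outline.
- **(b)** Residual viable index tumour, yes or no, classed as inside the planned zone on the KOELIS map (ablation failure) or outside it (coverage failure).

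Section 6.0 blinds the pathologist to MR and TRUS imaging. The pathologist should therefore outline tumour and record viability first; matching to the MRI lesion and the map follows as a separate step.

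Also define the TMA-treated zone in 6.0, and extend the 2.5 targeting comparison to ablation zone against index-lesion location. In 10.4, replace the count of ablations needed with coverage by template, shown beside MRI lesion diameter.

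Base any statement about the feasibility of ablating the index lesion on these results, with exact intervals and no test. Precision is modest: complete ablation in 5 of 5 gives a 95% interval of 0.025^(1/5) = 47.8% to 100%; in 10 of 10, 0.025^(1/10) = 69.2% to 100%. With one man per template in the immediate phase and two in the delayed phase, results by template are a listing.

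No added patients or procedures are needed. The cost is annotation and image overlay, and a result likely to look less favourable than in-zone necrosis.

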#### 4.2 Toxicities and Dosing Delays/Dose Modifications

We will monitor for TMA related toxicities such as rectal injury, bladder injury, and perineal pain. Complications will be managed with best supportive care. Since previous literatures have not adapted similar study design (TMA and immediately resect), we do not have standard dosage of TMA needed to ablate planned area on the prostate. Therefore, we start from low output and ablation time and escalate them in accordance with corresponding histologically ablated area.

---

According to the manufacturer's data based on other soft tissues, ablation coverages of short x long axis (cm) are estimated 1.5 x 2.5 for short-time (3min) ablation, 2.0 x 2.7 for medium-time (5min) ablation, and 2.5 x 3.0 for long-time ablation.

Based on the data, our TMA delivery strategy is planned as follows.

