### 5.3.4 Pathologic Evaluation

Following prostatectomy, the prostates will primarily be evaluated using standard-of-care diagnostic methods, and secondarily be assessed in accordance with the thermal treatment parameters. The intact prostate specimens should be received in pathology within two up to six hours of prostatectomy. Standard gross examination of prostate specimens will be done including measurement, appropriate inking for margins and serial transverse sectioning from the bladder neck across the prostate to the penile urethral margin. Digitally photographing of these sections will be done. TTC viability staining will be performed not less than 2 hours after TMA and 4 up to 6 hours after completion of prostatectomy. Macroscopic evaluation of the TTC stained sections will be performed where viable tissues would exhibit maroon color change, while ablated non-viable tissues should show absence of color change. Routine tissue processing and H&E staining will be performed. H&E stained whole mount sections of the prostatectomy specimens will be evaluated on microscopy. If indicated, IHC staining will be done.

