## 10.7 Data Analyses Plans

All patients who sign the consent form will be registered and entered the database. For each patient, we will list whether he received the assigned protocol (and if not, the reasons), the outcome of the procedures, compliance with the protocol (and reasons for failure to comply), adverse events with any of the procedures, MRI results, and targeted biopsy results.

- The data from the immediate resection phase and delayed resection phase will be separately evaluated. The observed ablated area in immediate resected prostatectomy specimen based on TTC staining will be compared with the predicted ablation area according to the template. The tissue viability will be evaluated by HE staining on delayed resection prostatectomy specimen.
- The comparison of the difference between the treatment effect dimensions measured histologically on the prostatectomy specimen resected after TMA and the predictive ablation charts provided by the manufacturer will be performed. For this analysis, the data from immediate resection phase and delayed resection phase are separately evaluated.
- The comparison between the treatment effect dimensions measured histologically on the prostatectomy specimen resected one month after TMA, compared to post TMA dimensions measured on the pre-RP mpMRI.
- To evaluate the intra/post-operative safety of TMA, we defined 30% as clinically acceptable severe adverse events (defined as CDC  $\geq 3$ ) rate. If the severe adverse events occur less than 30% (equivalent to less than 4 cases in 10 cases) for the delayed ablation phase, the feasibility of TMA is proved.

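### The reading pathologist is blinded to imaging only; nothing in the plan withholds the template, ablation time or predicted dimensions with which the reading is compared

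*Combined protocol and SAP*

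**What the plan says.** - **Blinding.** Section 6.0 states: "The pathologist will be blinded to MR and TRUS imaging results". This is the only sentence on blinding the histologic reading. Section 7.6 marks unblinding as not applicable.
- **What is read.** Section 6.0 defines the main effect as the share of dead tissue "inside the TMA-treated zone on the prostatectomy specimen". Section 2.4 names the primary endpoint as the ablated area by TTC staining.
- **What the reading is compared with.** Under Section 10.7 the observed TTC area in the immediate phase "will be compared with the predicted ablation area according to the template". For both phases, evaluated separately, a comparison of histologic dimensions with "the predictive ablation charts provided by the manufacturer will be performed".
- **What is available at assessment.** Sections 5.3.4 and 9.1, in identical wording, say that specimens will "secondarily be assessed in accordance with the thermal treatment parameters".
- **Predicted sizes.** Section 4.2 gives short by long axis in cm: "1.5 x 2.5 for short-time (3min) ablation, 2.0 x 2.7 for medium-time (5min) ablation" and "2.5 x 3.0 for long-time ablation".
- **Allocation.** There is no randomization (Section 5.2). Under Section 4.2, patients 1 to 5 receive Templates 1 to 5 in turn, and patients 6 to 15 receive them in consecutive pairs. The physician may modify delivery.
- **Photographs.** In Section 5.3.4, "Digitally photographing of these sections will be done" comes after gross sectioning and before the sentence on TTC staining.

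**The concern.** The plan shields the pathologist from MR and TRUS imaging. That protects the comparison of histology with the pre-prostatectomy mpMRI. It arguably also protects the comparison with the KOELIS 3D map, which is built from ultrasound. The same protection is not extended to the third comparator, the template and the manufacturer's chart.

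A reader who knows the template and the chart knows the size that the measurement is meant to test. Where a border is uncertain, that knowledge can draw the reading toward the expected value. What is at stake is the chart-predictability objective (Sections 2.2 and 2.5) and the immediate-phase comparison of TTC area with the template. Section 1.3 presents step-section histology with TTC as the gold standard, and a reference reading made with knowledge of the prediction is a weaker check on that prediction. Section 4.2 also uses the histologic area to guide escalation, so the reading matters during the trial as well as at the end.

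**Working it through.** The plan states no figure for reader bias, so there is nothing to reproduce. The check is a comparison of the text, plus arithmetic on the Section 4.2 dimensions to give scale.

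**1. Which comparators does the blinding cover?**

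| Histology compared with | Source | Withheld from the pathologist? |
|---|---|---|
| Pre-prostatectomy mpMRI | 2.5, 10.7 | Yes (6.0) |
| KOELIS 3D map (location) | 2.5, 10.7 | Arguably yes, as TRUS-based (6.0) |
| Template's predicted area | 10.7 | Not stated |
| Manufacturer's chart dimensions | 2.5, 10.7 | Not stated |

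Sections 5.3.4 and 9.1 tie the pathology assessment to the treatment parameters. The wording is loose, but it leans toward the parameters being at hand.

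**2. For whom does the expected size follow from the template?** Section 4.2 gives dimensions for single ablations only, so this covers Templates 1 to 3 (taking the long-time ablation as the 7.5-minute one).
- Templates 1 to 3: patients 1, 2, 3 and 6 to 11, so 3 + 6 = 9 of 15.
- Templates 4 and 5 (overlapped double ablations): patients 4, 5 and 12 to 15, so 2 + 4 = 6 of 15. The readable text gives no predicted size for these. The appendix on delivery strategy is not readable here and may hold one.

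For the 9 men, the patient's order number normally gives the template and hence the size, unless delivery was modified (4.2), a patient was replaced (4.7) or numbers were extended (10.6).

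**3. How far apart are the predicted sizes?** Area is taken as an ellipse, π/4 × short × long (an assumption about shape).

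| Ablation | Short × long (cm) | Area (cm²) |
|---|---|---|
| Short | 1.5 × 2.5 | 0.7854 × 3.75 = 2.95 |
| Medium | 2.0 × 2.7 | 0.7854 × 5.40 = 4.24 |
| Long | 2.5 × 3.0 | 0.7854 × 7.50 = 5.89 |

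- Short-axis steps: 2.0 − 1.5 = 0.5 cm and 2.5 − 2.0 = 0.5 cm, so 5 mm each.
- Long-axis steps: 2.7 − 2.5 = 0.2 cm and 3.0 − 2.7 = 0.3 cm, so 2 mm and 3 mm.
- Slice interval (6.0): 4 mm.

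The long-axis steps are smaller than one slice interval and the short-axis steps slightly larger. Across slices, a border decision of about one slice is of the same order as the step from one chart entry to the next. Within a slice, resolution may be finer.

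**4. Direction.** Let t be the true dimension, p the predicted one, and w the fraction by which a reading is drawn toward p. The reading is t + w(p − t), so the reported discrepancy is (1 − w)(t − p). For any w between 0 and 1 the discrepancy shrinks toward agreement. The documents give no value for w and no figure for t − p, so the amount cannot be calculated. The mean of n such discrepancies is (1 − w) times the mean true discrepancy, whatever n is.

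**The case against.** The strongest reply is that silence is not disclosure. No section says that the pathologist receives the template, the ablation time, the chart or the enrolment number. That stands. A reader might infer that the pathologist reads with the prediction in hand; the documents support only that nothing prevents it and that Sections 5.3.4 and 9.1 point that way.

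Other parts of the reply also stand:

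- **Not every size is deducible.** For 6 of 15 men the readable text gives no predicted dimensions.
- **The primary result is not shown to be biased in a known direction.** A reader might infer that the proportion of dead tissue is inflated. Section 6.0 does not say how the treated zone is delimited. Drawing it at the chart size could lower the proportion if the ablation fell short, and following the stain could raise it.
- **No stated conclusion is shown to change.** Section 10.7 sets no threshold for agreement with the chart. Its only feasibility criterion is the severe adverse event rate, which this point does not touch.
- **Sample size is not the cause.** One might think that one man per template makes the bias worse because nothing averages it out. A systematic pull does not average out with more men either.
- **TTC is described as a clear colour contrast.** Sections 1.3 and 5.3.4 report maroon viable tissue against unchanged ablated tissue, and give no evidence of ambiguous borders. Equally, no border rule or second reader is described.
- **Coding is imperfect.** Men in the immediate phase are treated one at a time (7.7), so arrival order stays visible. Templates 1 and 2 treat both lobes and Templates 3 to 5 one, which the specimen may show.

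These points limit the claim and the size that can be put on it. They do not close the gap between what is blinded and what is compared.

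**Conclusion.** The point holds in a limited form. The only blinding rule covers imaging, while the template and chart predictions, which are comparators in Section 10.7, are not withheld. For the single-ablation templates the expected size follows from the template, and the template normally follows from patient order. If the reader knows it, any pull is toward the chart and makes the chart-predictability comparison look better than it is.

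This rests on two assumptions: that the reader can learn the template or parameters, which the text permits but does not state, and that some borders leave room for judgement. The size of the bias cannot be derived from the documents. The 2 to 5 mm steps between predicted dimensions and the 4 mm slice interval show scale only; they do not estimate the bias. It is a cheap improvement to an exploratory study, not a demonstrated error in its results.

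**What to change.** 1. **Section 6.0.** Extend the blinding sentence: the reading pathologist is not given the template, power, ablation time, enrolment number or predicted dimensions until the zone borders and dimensions are recorded and locked for that patient. They are then released for the comparison and the escalation review. Locking patient by patient keeps the reading available during the trial, as Section 4.2 requires.
2. **Section 6.0, zone definition.** State how the border of the treated zone is drawn without those values.
3. **Sections 5.3.4 and 9.1.** Reword the clause on thermal treatment parameters so that they are used after the lock; otherwise these sections would contradict 6.0.
4. **Photographs.** Take or repeat them after TTC staining, so that locked borders can be checked. As Section 5.3.4 is ordered, they may not show the stain.

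The cost is specimen coding, a lock step and possibly a second set of photographs; no extra reader or patient is needed. The TTC timing limit requires the laboratory to know when ablation ended, not how long it lasted or which template was used, and routine diagnostic pathology is unaffected. Arrival order in the immediate phase and bilateral versus one-sided treatment stay partly recognisable, so the change reduces the exposure without removing it.
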